9.3.4.8 Safety Reporting Requirements

Each AE is to be classified by the Investigator as serious or non-serious. This classification will determine the reporting procedure for the event.

All SAEs are to be reported immediately (within 24 hours of awareness of the SAE by the Investigator), to [contact], using the SAE report form. This includes a

description of the event, onset date and type, duration, severity, relationship to each of the IMPs, outcome, measures taken and all other relevant clinical and laboratory data.

The initial report is to be followed by submission of additional information (follow-up SAE form) as it becomes available. Any follow-up reports should be submitted as soon as possible, and if possible within 5 working days from awareness of the information by the Investigator.

SAEs should also be reported on the AE page of the eCRF. It should be noted that the form for reporting of SAE (SAE form) is not the same as the AE section of the eCRF. Where the same data are collected, the two forms must be completed in a consistent manner, and the same medical terminology should be used.

In addition to immediately reporting SAEs to DNDi, the Investigator will immediately notify the regulatory authorities and ethics committee(s) of SAEs (and non-serious AE if required by the local regulatory requirements), and follow-up information, that occur during this trial, if applicable, in accordance with the standard operating procedures/guidelines/regulations issued by the regulatory authorities and ethics committee(s).

A suspected unexpected serious adverse reaction (SUSAR) is a suspected AE related to an investigational medicinal product that is both unexpected and serious.

DNDi, the Sponsor is responsible for determining the expectedness of the event for each IMP, using the reference safety information defined for the study, contained in the Investigator Brochure for ABBV-4083, and in the Prescribing Information for albendazole and ivermectin. ^{57,63,65}

DNDi will notify the regulatory authorities and ethics committee(s) of all SUSARs (if applicable based on local requirements) in compliance with local safety reporting requirements.

If unblinding is required for expedited reporting (as per local requirements), reporting of SUSARs to the regulatory authorities and ethics committee(s) will not involve any personnel at the investigational centre or other members of the Sponsor's study team, to preserve the study blind.

9.3.4.9 Exposure in utero

If a trial subject becomes or is found to be pregnant (based on date start last menstruation period) while receiving any IMP or within 1 month of discontinuing the IMP, the Investigator must submit the event on a "Pregnancy Surveillance Form" in accordance with the same process and timelines as defined for SAEs (see Section 9.3.4.8).

This must be done irrespective of whether an AE has occurred. The information submitted should include the start date of last menstruation period (or the best estimation) and the anticipated date of delivery.

The Investigator will follow the subject until completion of the pregnancy or until pregnancy termination (i.e. induced / spontaneous abortion). The Investigator will provide pregnancy follow-up or outcome information on a "Pregnancy Surveillance Form".

In the case of a live birth, a medically qualified person (preferably a paediatrician) should assess the infant at the time of birth and submit a "Child Surveillance Form". The Investigator will offer the parents follow-up on infants exposed to the study treatment in utero until they reach 24 months of age.

A pregnancy is not a SAE. Any unfavourable outcome meeting at least one seriousness criteria i.e. in the case of unfavourable pregnancy outcome (spontaneous and induced abortion, still

birth) or congenital abnormality shall be reported using the "SAE form" (in addition to the Pregnancy/Child Surveillance Form).

9.3.4.10 Adverse Event Follow-up

All AEs should be followed until:

- they are resolved; or
- the Investigator assesses them as "chronic" or "stable"; or
- the subject's participation in the trial ends, i.e. as defined in Section 3.4.

The Principal Investigator or Co-investigator may or will interrupt or suspend treatment due to serious safety issues in order to protect the subjects. In addition, all SAEs, whether related or not, must continue to be followed even after the subject's end of study participation in order to collect the outcome. Such events should be followed until they resolve or until the Investigator assesses them as "chronic" or "stable." Resolution of such events is to be documented on the AE page of the eCRF (up to the end of study participation) and SAE form (up to and after the end of study participation).

For SAEs that occur after the subject's end of study participation, see Section 9.3.4.8.

9.3.4.11 Overdose

All overdoses with the study treatment will be recorded in the eCRF. If the overdose is symptomatic and clinically significant, it will also be reported as an AE.

In the event of an overdose with the study treatment, symptomatic and supportive therapy should be given as appropriate, and the Investigator should contact the Sponsor's Medically Responsible Person.

Medication errors with the study treatment committed by study personnel that result in a possible overdose, as well as all medication errors, must be documented as protocol deviations and reported to the Sponsor and the regulatory authorities and ethics committee(s) if required in accordance with the requirements of the local ethics committee(s) and regulatory authorities.

9.3.4.12 Monitoring of AEs Outside the Investigational Centre

To ensure appropriate and timely management of AEs, a process will be set up for reporting and communication of any AEs that occur when the subject is not at the investigational centre. The process will be described in the Study Operations Manual/SOPs.

10 Statistical Analyses

10.1 Statistical Hypotheses

10.1.1 Primary Hypothesis in Part 1

The primary hypothesis for the proof of concept in Part 1 is that more worms will have *Wolbachia* depletion at 6 months in the subjects who completed treatment with ABBV-4083 for 7 days (Arm A), ABBV-4083 for 14 days (Arm B), ABBV-4083 + albendazole for 7 days (Arm C), or ABBV-4083 for 7 days + albendazole for 3 days (Arm D) than in subjects treated

with albendazole for 7 days (Arm E) among all subjects who completed treatment and who had live female worms from nodulectomies at 6 months.

The primary hypothesis to satisfy the combination rule in Part 1 is that more worms will have *Wolbachia* depletion at 6 months in the subjects treated with ABBV-4083 + albendazole for 7 days (Arm C) than in subjects treated with albendazole for 7 days (Arm E) or those treated with ABBV-4083 for 7 days (Arm A) among all subjects who completed treatment and had live female worms from nodulectomies at 6 months. If the combination arm of ABBV-4083 for 7 days + albendazole for 3 days (Arm D) is to advance to Part 2 and ABBV-4038 for 7 days + albendazole for 7 days (Arm C) is not, then the combination rule will be tested for ABBV-4083 for 7 days + albendazole for 3 days (Arm D) in Part 1. Of note, the possible substitution of ABBV-4083 for 7 days plus albendazole for 3 days in place of ABBV-4038 + albendazole for 7 days will not be continuously noted below for brevity sake.

10.1.2 Primary Hypotheses in Part 2

The primary hypothesis for Part 2 is that more subjects treated with one or more of the active regimens selected from Part 1 (Arms K, L and M) will be without skin microfilariae at 24 months as compared to subjects treated with placebo (Arm N1, base scenario) or ABBV-4083 for 7 days (Arm N2, alternate scenario).

Combination Rule Hypothesis for Part 2 Alternative Scenario

If the primary hypothesis to satisfy the combination rule in Part 1 is not satisfied and ABBV-4083 + albendazole for 7 days (Arm C in Part 1) is to be carried forward to Part 2 (as either Arm K with ivermectin and Arm L without ivermectin, or as Arm M with or without ivermectin), an additional hypothesis using appropriate subjects from both Part 1 and Part 2 will be that more worms will have *Wolbachia* depletion at 6 months in subjects treated with ABBV-4083 + albendazole for 7 days (Arm C for Part 1 and Arm K plus Arm L [or alternately Arm M if appropriate] for Part 2) than in subjects treated with ABBV-4083 for 7 days (Arm A for Part 1 and Arm N2 for Part 2) among all subjects who completed treatment and who had live female worms from nodulectomies at 6 months.

In the case that ABBV-4083 for 7 days + albendazole for 3 days (Arm D in Part 1) is selected for Part 2 and ABBV-4083 + albendazole for 7 days (Arm C in Part 1) is not selected, and the primary hypotheses for satisfying the combination rule in Part 1 are not satisfied, then the arm or arms containing ABBV-4083 for 7 days + albendazole for 3 days will be treated as described elsewhere in this document for ABBV-4083 + albendazole for 7 days in the Alternate Scenario, and the data combined with Arm D in Part 1 for analysis.

10.1.3 Key Secondary Hypotheses in Part 2

The key secondary hypotheses in Part 2 are as follows:

- The first secondary hypotheses for Part 2 (Endpoint 2a) are that a smaller mean percentage of female adult worms per subject will be alive at 24 months among the subjects who completed treatment with one or more of three assigned regimens selected from Part 1 (Arms K, L and M) compared to either placebo (Arm N1) or ABBV-4083 for 7 days (Arm N2).
- The second secondary hypotheses for Part 2 (Endpoint 2b) are that a larger mean percentage of live female adult worms will have only degenerated embryos in their uteri

per subject at 24 months among the subjects who completed treatment with one or more of three regimens selected from Part 1 (Arms K, L and M) compared to either placebo (Arm N1) or ABBV-4083 for 7 days (Arm N2).

10.2 Analysis Sets

The analysis sets are:

- Intention-to-treat (ITT) population: all randomised subjects who received at least one dose of IMP.
- Primary population for Part 1 primary endpoint and Part 2 combination rule endpoint for Alternative Scenario: Per protocol (PP) for nodulectomy at 6 months (ND6M), i.e. all ITT subjects who had Month 6 nodulectomy with live female adult worms, who completed treatment and who did not take prohibited medication during the study (see Appendix 8 Sections II and IV).
- Primary population for Part 2 proportion of subjects with microfilaria depletion at Month 24 endpoint: PP population for microfilaria, defined as all subjects in the ITT population who had microfilaria-positive skin-snips at baseline, who completed treatment, had skin snips at Month 24 or received ivermectin rescue before Month 24, and who did not take prohibited medication during the study (see Appendix 8 Sections II and IV).
- Primary population for Part 2 secondary endpoints 2a: PP population for nodulectomy at 24 months (ND24M), i.e. all ITT subjects who had Month 24 nodulectomy with female adult worms, who completed treatment and who did not take prohibited medication during the study.
- Primary population for Part 2 secondary endpoints 2b: PP population for nodulectomy at 24 months (ND24M) with live female adult worms, i.e. all ITT subjects who had Month 24 nodulectomy with live female adult worms, who completed treatment and who did not take prohibited medication during the study.
- Safety population: all randomised subjects who received at least one dose of IMP.

Subjects who take prohibited medications that may have an impact on the study objectives (Appendix 8- sections II and IV) are excluded from the PP populations. Specifically subjects who take medications with an anti-filarial or anti-Wolbachia effect at any time during the study (Appendix 8-section II) or strong CYP3A inducers or dexamethasone during the treatment period that may lower ABBV-4083 or albendazole exposures (see Appendix 8 - Section IV) are excluded from the PP population.

Completed treatment for Part 1 is defined as taking at least 6 out of 7 days of randomised ABBV-4083, ABBV-4083 + albendazole or albendazole alone (Arms A, C or E, respectively), 12 out of 14 days of randomised ABBV-4083 (Arm B) or 6 out of 7 days of randomised ABBV-4083 and all of 3 days of randomised albendazole (Arm D). The same definitions of treatment completion will be applied to the similar arms in Part 2, except that subjects must also be administered ivermectin or matching placebo at Month 6 to be considered as having completed treatment.

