4.1 Primary Objectives

The primary objectives are to:

Part 1:

- determine whether treatment with ABBV-4083 or ABBV-4083 + albendazole effectively depletes *Wolbachia* bacteria in adult female worms at Month 6 by immunohistology;
- establish the superiority of ABBV-4083 + albendazole to each drug alone according to the depletion of *Wolbachia* bacteria in adult female worms at Month 6 by immunohistology

Part 2:

- determine whether treatment with ABBV-4083 or ABBV-4083 + albendazole effectively eliminates microfilariae from the skin at 24 months.
- if superiority of 7-day treatment with ABBV-4083 + albendazole to 7 days of ABBV-4083 is not established in Part 1, the Alternate Scenario of Part 2 (see Section 3.3) has the additional objective to establish that a combination of ABBV-4083 + albendazole is superior to ABBV-4083 alone by combining data from Parts 1 and 2.

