8.1 Prior and Concomitant Medication

The prior medication listed below will be recorded in the source documents and eCRF. See Section 6.2 for exclusion criteria based on concomitant medication.

- All prior anthelminthic treatments or medication given for onchocerciasis including ivermectin or albendazole alone or in combination, doxycycline, minocycline, rifampicin, rifapentine, moxidectin, praziquantel or mebendazole, including date of last intake.
- Doxycycline for other indications, within 1 year prior to IMP administration
- Vaccinations, within 4 weeks prior to IMP administration
- All other prior medication, including contraceptives, and preventive chemotherapy, herbal preparations or food supplements taken within 1 month before the start of Screening at the investigational centre
- Other currently effective contraceptive medication or devices, including long-acting depot or implantable preparations containing sex hormones or intra-uterine devices, (see also Section 8.2)

From signature of ICF onwards, subjects will be instructed not to take any medications, traditional medicines or herbal preparations by themselves at any time during the study (with the exception, where relevant, of contraceptives allowed by protocol).

During the study, if the subject requires treatment, the Investigator should be informed and approve the proposed medication in line with the following instructions:

Throughout the entire study, the use of medication that may have an impact on the study objectives is not permitted.

- In addition, up to 24 hours after the final dose of IMP, no medication, including herbal remedies or food supplements and preventive chemotherapy (MDA), other than the IMPs, rescue medication and permitted medication described in this section is allowed unless absolutely necessary for treatment of AEs or the symptoms of onchocerciasis (see Appendix 8 for the list of prohibited medication during the trial).
- Permitted medications, as an exception, include:
 - · diclofenac, paracetamol, ibuprofen, and aspirin
 - contraceptives (see Section 8.2) for WOCBP
 - topical drugs required for the eye examinations (e.g. mydriatic eye drops, anaesthetic drops)

The following information will be recorded (along with the details as specified in Section 9.3.1.3):

- Medications taken between signature of ICF and the end of study participation (see Section 3.4) must be recorded in the source documents and eCRF.

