Appendix 8. Prohibited medications in DNDi-TYL-01

I. Prohibited medication before starting the study (see also Section 6.2)

- within 2 years prior to start of IMP administration: moxidectin;
- within 1 year prior to start of IMP administration: more than 2-week course of anti-Wolbachia treatments, i.e. doxycycline, minocycline, rifapentine or rifampicin;
- within 6 months prior to start of IMP administration: ivermectin;
- within 3 months prior to start of Screening (or within 5 times the half-life of the drug tested): any investigational drug;
- within 4 weeks prior to start of IMP administration: any vaccination;
- Within 14 days prior to start of IMP administration:
 - o any medication (with the exception of diclofenac, paracetamol, ibuprofen and aspirin), herbal preparation or food supplement;
 - o strong CYP3A inhibitors or inducers including but not limited to ritonavir^c, ketoconazole^c, rifampicin, phenytoin, phenobarbital, carbamazepine, cimetidine^c (or within 10 half-lives, whichever is longer);
 - o other drugs known to interact with albendazole such as praziquantel^c, theophylline^c or dexamethasone^c (or within 10 half-lives, whichever is longer);

II. Prohibited medication throughout the entire study^a

Prohibited medication throughout the entire study include any medication that may have an impact on the study objective. Specifically, medication with anti-filarial or anti-Wolbachia effects are prohibited, including:

- ivermectin, excluding post-study ivermectin or rescue ivermectin as detailed in Section 8.3.
- moxidectin,
- doxycycline,
- minocycline,
- rifampicin,
- rifapentine.

III. Prohibited medications during the first 28 days after the last IMP administration

Albendazole (however it is permitted thereafter, one dose per year in MDA)

IV. Prohibited medication during the treatment period

Up to 24 hours after the final dose of IMP, medication, herbal remedies or food supplements, that could affect the PK and/or PD of ABBV-4083 and/or albendazole are prohibited.

- Any CYP3A and/or P-gp inhibitors or inducers, such as:
 - o ritonavirc,
 - o ketoconazolec,
 - o rifampicin^b,
 - o phenytoin^b,
 - phenobarbital^b,
 - carbamazepine^b,
 - o cimetidinec,
 - o others known to interfere with the CYP3A and/or P-gp metabolic pathways (the US FDA tables of Substrates, Inhibitors and Inducers^b will be used as a reference, and included in the Study Operations Manual for reference).
- Drugs known to interact with albendazole, such as

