 - o praziquantelo,
 - o dexamethasone^b
 - o theophylline^c
- a. Subjects taking these medications during the study will not be included in the PP population for analysis and will be imputed as failures in analyses of the primary and secondary endpoints in the ITT population.
- b. Subjects taking these medications during the treatment period (or for 14 days before) will not be included the PP population for analysis but will not be imputed as failures in analyses of the primary and secondary endpoints in the ITT population.
- c. Subjects taking these medications during the treatment period (or for 14 days before) will be included in the PP population for analysis and will not be imputed as failures in analyses of the primary and secondary endpoints in the ITT population.

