## 4.0 Analysis Populations

The following population sets will be used for the analyses.

The Intention-to-Treat (ITT) population includes all randomised subjects who received at least one dose of study drug. The ITT population will be used for all non-primary efficacy estimands. Subjects will be included in the analysis according to the treatment arm to which they were randomised.

The Per-Protocol (PP) population will include all ITT subjects who had Month 6 nodulectomy (ND6M) with live female adult worms, who completed treatment and did not take prohibited medication(s) during the study. Treatment completion is defined as taking at least 6 out of 7 days of ABBV-4083 in Arm A, 12 out of 14 days of ABBV-4083 in Arm B, 6 out of 7 days of ABBV-4083 + albendazole in Arm C, 6 out of 7 days of ABBV-4083 and all 3 days of albendazole in Arm D, and 6 out of 7 days of albendazole in Arm E. Prohibited medications (Appendix B) include those with anti-filarial or anti-*Wolbachia* effect taken at any time during the study, or strong CYP3A inducers or dexamethasone taken during the treatment period. The PP population will be used as the primary population for testing the two primary hypotheses (Section 2.1).

The Safety population includes all randomized subjects who received at least one dose of study drug. Subjects will be included in the analysis according to treatment as randomized. The Safety population is the same as the ITT population.

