#### Appendix B. List of Prohibited Medications

The following medications are prohibited throughout the entire study because of their anti-filarial or anti-Wolbachia effects:

- ivermectin (excluding protocol-defined, post-study ivermectin mentioned in Section 2.2)
- moxidectin,
- doxycycline,
- minocycline,
- rifampicin,
- rifapentine.

The following medications are prohibited during the treatment period, up to 24 hours after the final dose.

- Any CYP3A and/or P-gp inhibitors or inducers, such as:
  - rifampicin,
  - phenytoin,
  - phenobarbital,
  - carbamazepine,
  - others known to interfere with the CYP3A and/or P-gp metabolic pathways (the US FDA tables of Substrates, Inhibitors and Inducers will be used as a reference, and included in the Study Operations Manual for reference).
- Dexamethasone is known to interact with albendazole and will also be prohibited during the treatment period, up to 24 hours after the final dose.

Any subject who takes a prohibited medication during the study will be documented via a protocol deviation, which will be used to determine eligibility for the per-protocol population.

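### Non-study albendazole has no stated analysis consequence, so a subject who takes it can stay in the primary combination-rule contrast as ABBV-4083 alone

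*Protocol*

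**What the plan says.** One primary objective in Protocol 4.1 is to "establish the superiority of ABBV-4083 + albendazole to each drug alone". In Part 1 it is tested in the PP population by C v A and C v E, or by D v A and D v E if only Arm D advances.

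Protocol 10.2 and 10.4 tie PP exclusion to two sections of Appendix 8: "Appendix 8- sections II and IV) are excluded from the PP populations". For Section IV, Protocol 10.2 narrows this to "strong CYP3A inducers or dexamethasone during the treatment period that may lower ABBV-4083 or albendazole exposures". Albendazole stands alone in Section III, which covers the 28 days after the last IMP: "Albendazole (however it is permitted thereafter, one dose per year in MDA". None of the footnotes a, b or c, which set the analysis consequences, is attached to it.

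The Part 1 SAP follows the same pattern. Section 4.0 excludes users of anti-filarial or anti-*Wolbachia* drugs and "strong CYP3A inducers or dexamethasone taken during the treatment period". SAP Appendix B lists the drugs without naming albendazole. It adds that use of a prohibited drug is recorded as a deviation, "which will be used to determine eligibility for the per-protocol population".

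**The concern.** Albendazole is the component whose added value is under test, so the comparator in C v A and D v A needs to be free of it. As written, a subject who takes dexamethasone leaves the PP set because albendazole exposure might fall, while an Arm A subject who takes albendazole itself stays. Short exposure is not something the protocol dismisses. Section 2.4.3 bases Arm D on jird data in which 3 days of albendazole alongside 7 days of ABBV-4083 gave a strong signal.

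If a combination arm is selected but the rule is missed in Part 1, the Alternate Scenario follows: 336 subjects instead of 294, comparator N2 instead of placebo, and a Month 6 nodulectomy subset. The Part 1 p-value is then reused in the Part 2 inverse normal test (Protocol 10.5), so a diluted Part 1 contrast carries forward.

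The planned tables would not show the problem. SAP 7.3 does not count a drug started after the last study dose as concomitant, so albendazole taken after discharge is left out of that summary. The data exist, because Protocol 8.1 records medication to the end of study participation.

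**Working it through.** **1. What each on-study section of Appendix 8 leads to**

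| Section | PP | ITT |
|---|---|---|
| II: anti-filarial and anti-*Wolbachia* drugs | excluded (a) | counted as failure |
| III: albendazole | not stated | not stated |
| IV: CYP3A inducers, dexamethasone | excluded (b) | not a failure |
| IV: ritonavir, ketoconazole, cimetidine, praziquantel, theophylline | kept (c) | not a failure |

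Footnote c is explicit that these users "will be included in the PP population for analysis and will not be imputed as failures in analyses of the primary and secondary endpoints". Only Section III is silent.

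**2. When the gap applies**

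In Part 1 every arm takes capsules on Days 0 to 13, so the prohibited window ends on Day 13 + 28 = Day 41. After that, a yearly MDA dose is allowed, including before the Month 6 nodulectomy. Arm A's active ABBV-4083 ends on Day 6, and subjects are in-house through Day 13. Use after discharge therefore starts at least 14 − 6 = 8 days after the last active dose. In Part 2, Protocol 6.1 and 8.2 treat the Month 6 ivermectin or placebo as the final IMP intake, so a window counted from the last IMP would run to about Month 7.

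**3. Power of C v A**

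Inputs (Protocol 10.3.1): 25 subjects per arm; 90% v 70% of worms without *Wolbachia*; ICC 0.01 and 0.54; worms per subject from 1 to 10 with the stated probabilities (mean 3.79); 2-sided α = 0.10; stated power 81%.

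Model: subject rate q ~ Beta(pκ, (1 − p)κ) with κ = (1 − ICC)/ICC, that is 0.46/0.54 = 0.85 for Arm A and 0.99/0.01 = 99 for Arm C; worms without *Wolbachia* ~ Binomial(m, q).

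Test: z = (logit P_C − logit P_A) / √(V_C/[P_C(1 − P_C)]² + V_A/[P_A(1 − P_A)]²), where P is the pooled worm proportion and V its cluster-robust variance. Reject if |z| > 1.645. This stands in for alternating logistic regression, which was not run.

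Plan figure first: 81.2% (80.4% with a √(24/25) small-sample factor), which reproduces 81%.

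Assumed contamination: on average k of 25 Arm A subjects take albendazole. At full effect they behave like Arm C (90%, ICC 0.01), so the control rate is 0.70 + 0.20 × k/25. At half effect they respond at 80% with ICC 0.54. The odds ratio (OR) is (0.90/0.10) ÷ (rate/(1 − rate)). Each row uses 40,000 simulated trials.

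| k | Control rate, full effect | OR | Kept, full effect | Kept, half effect | Excluded |
|---|---|---|---|---|---|
| 0 | 70.0% | 3.86 | 81.2% | 81.2% | 81.2% |
| 1 | 70.8% | 3.71 | 79.4% | 79.6% | 80.4% |
| 2 | 71.6% | 3.57 | 76.9% | 78.8% | 78.8% |
| 5 | 74.0% | 3.16 | 69.0% | 75.2% | 76.2% |

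The small-sample factor lowers each power by about 1 point. Exclusion gains 1.0, 1.9 and 7.2 points at full effect, and 0.8, 0.0 and 1.0 at half effect.

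Limits: weighting worms by an exchangeable correlation gives a baseline of about 84% with the same pattern. That variant matches the plan's other power figure (88% for proof of concept) but not the 81%, and neither variant matches both.

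**The case against.** The strongest reply is that contamination is unlikely and its effect small. Part 1 dosing is in-house and directly observed. Protocol 8.1 allows, until 24 hours after the final dose, "no medication, including herbal remedies or food supplements and preventive chemotherapy (MDA), other than the IMPs" and listed exceptions. Exclusion criterion 5 removes people who need albendazole in the first 28 days. After discharge, ABBV-4083 (half-life under 4 hours) has long gone, and Protocol 2.4.1 treats albendazole alone as close to no treatment for efficacy. Giving a late stray dose the full Arm C response has no support in the documents. All of this stands, and it is why the power table is only an illustration.

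A second reply is that existing text already covers the case. Section II opens with any drug that may affect the study objective, and SAP Appendix B routes deviations into PP eligibility. This stands only in part. Section II goes on to name anti-filarial and anti-*Wolbachia* drugs without albendazole, Section III exists separately, and Appendix B does not name it either. Two analysts could build different PP sets for a primary contrast.

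A reader might also infer that albendazole is the only prohibited drug without an analysis consequence. Footnote c contradicts that: several Section IV drugs have an explicit rule that keeps their users in PP. Albendazole differs in having no rule at all.

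**Conclusion.** The gap is real and worth closing. Section III is the only on-study section whose analysis consequence is never stated, and the literal rule keeps an albendazole user in Arm A, or in N2 under the protocol rule, as ABBV-4083 alone.

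The result is a possible bias in C v A and D v A, not a demonstrated one. It needs actual use in the window and an effect of that use, and the documents give neither. A reader might infer that the comparator is in fact diluted, or that a false combination claim could follow. The documents support neither reading. If stray albendazole acts at all in the direction the trial hypothesises, it moves Arm A towards Arm C and makes the rule harder to meet. The Alternate Scenario also gives a second test, with stated overall power of 95% to 96% (Protocol 10.3.2).

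Nor is recovered power the main reason to act. With 1 or 2 users in 25, exclusion gains about 1 to 2 points at full effect and 0 to 1 at half effect. The main reasons are a comparator that matches its label and a PP set fixed by rule. The SAP covers Part 1 only, so for N2 the finding rests on the protocol text.

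**What to change.** - **Protocol 10.2 and 10.4:** add Appendix 8 Section III to the PP exclusion for the combination-rule analysis. Define the analysis window as Day 0 to 28 days after the last dose of the initial ABBV-4083/albendazole (or matching placebo) course, and say that it does not run from the Month 6 ivermectin or placebo. Counted from that later dose, it would remove Part 2 subjects who took the yearly MDA dose the protocol allows.
- **ITT:** state that these subjects are analysed as observed.
- **SAP:** carry the same text into Part 1 SAP 4.0 and Appendix B, and into the separate Part 2 SAP.
- **Sensitivity:** leave the later yearly MDA permission unchanged. Add one run of C v A and D v A (and of combination v N2 in the Alternate Scenario) without subjects who took any non-study albendazole before the Month 6 nodulectomy.

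This changes analysis text only, not what subjects may take. The cost is a few lines in each document and one extra run on data already recorded. The downside is small: a few subjects may leave the PP set.
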